The potential benefit of oral decontamination in the treatment of COPD remains unknown. We have compelling evidence that the COPD lung microbiota is more diverse than healthy lungs and is a reflection of the oral microbiota, presumably due to repeated aspiration and decreased clearance. In addition, it is well established that bacteria are a major cause of COPD exacerbations. Therefore, it seems plausible that the oral microbiota is a major contributor in COPD and especially in COPD exacerbations. Chlorhexidine is a broad-spectrum antiseptic that is safe, well-tolerated and shown to decrease respiratory infection associated with oral intubation. We hypothesize that twice daily oral rinses with chlorhexidine will result in a decrease in the lung microbiota biomass. If proven correct, this would be the basis for a large interventional trial to determine if oral decontamination with chlorhexidine will decrease COPD exacerbations.

C. Work Proposed

Overview

The *primary outcome* of this pilot study is to determine if twice-daily chlorhexidine oral rinse decreases the microbiota biomass, as measured by 16S rRNA copy number, in the COPD lung and oral cavity as measured in induced sputum and oral wash. Our *secondary outcome* are to determine if chlorhexidine oral rinse: i) decreases lung and oral microbiota diversity; ii) alters taxonomic composition of the lung and oral cavity microbiota; iii) decreases systemic inflammation as measured by blood hsCRP, fibrinogen and leukocyte count; and iv) changes in respiratory health status as measured by the BCSS and SGRQ. If our hypotheses are supported, this study will form the basis of an interventional trial to determine if altering the oral microbiota with chlorhexidine can prevent COPD exacerbations.

Study Design Overview

This study will determine if the microbiota of the oral cavity and induced sputum is altered by twice-daily chlorhexidine rinse. At *baseline*, the following studies will be done:

1. Spirometry to determine study eligibility and to guide sputum induction protocol.
2. Oral rinse and induced sputum for microbiota analysis. An oral rinse of 15 ml sterile water and induced sputum will be obtained at baseline for microbiota analysis.
3. Inflammatory markers (blood hsCRP, fibrinogen, and leukocyte count).
4. Breathlessness, Cough and Sputum Scale (BCSS). This 3-item self-completed questionnaire focuses on common COPD symptoms.

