5. St George's Respiratory Questionnaire (SGRQ). This 50-item self-completed questionnaire quantifies respiratory health status.

After baseline measurements have been obtained, subjects will be randomized to 8 weeks of treatment with either twice daily oral rinse and expectoration of 15 ml of chlorhexidine or twice-daily oral rinse and expectoration of 15 ml of placebo (sterile water with mint flavor and blue dye). At the end of 8 weeks the subjects will have a repeat of the above studies, with the exception of spirometry.

Population and Setting

Participants with a clinical diagnosis of COPD who express willingness to participate in the trial and who fulfill all eligibility criteria will be enrolled in the study. To maximize sputum collection, we will enrich our population with COPD patients with symptoms of chronic bronchitis and a history of a COPD exacerbation in the past year. Patients with these characteristics are prone to having a larger volume of sputum production.

Inclusion and Exclusion Criteria:

• Inclusion Criteria

- Willingness to undergo *sputum induction*
- Capability to provide written informed consent
- Age ≥ 40 years and ≤ 85 years
- FEV₁/FVC ratio (post bronchodilator) $\leq 70\%$
- FEV₁ (post bronchodilator) $\leq 65\%$
- Presence or high likelihood of chronic cough and sputum production defined as **one** of the following:
 - Presence of chronic cough and sputum will be defined by responses to the first two questions on the SGRQ. Subjects who respond positively to both question 1 (cough) and question 2 (sputum) on the SGRQ as either “several days per week” or “almost every day” will be eligible.
 - COPD exacerbation within the previous 12 months defined as taking antibiotics and/or prednisone for respiratory symptoms, hospitalization or emergency department visit for respiratory illness.
- Current or former smoker with lifetime cigarette consumption of ≥ 10 pack-years
- Negative serum pregnancy test at the baseline visit if patient is a pre-menopausal female (menopause defined as absence of a menstrual cycle in the last 12 months)
- Must be fluent in speaking the English language
- Have a minimum of four teeth

• Exclusion Criteria:

- Not fully recovered for at least 30 days from a COPD exacerbation.
- Treated with antibiotics in the last 2 months.
- The presence of dentures (full plate).
- Active oral infection being treated by health care professional.

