Study participants will be randomized to receive either 15 ml oral rinse of chlorhexidine twice daily, or matched placebo (placebo consists of sterile water with blue dye and mint flavor). Participants will use the randomly assigned study mouth rinse for 8 weeks. At the initial visit, individuals participating in the study will undergo spirometry, SGRQ and blood sample for hsCRP followed by an oral rinse with sterile saline and sputum induction prior to initiating study drug. After 8 weeks of study drug, subjects will have all samples collected again (spirometry, SGRQ, blood draw, oral rinse, and induced sputum). Briefly, sputum will be induced after pretreatment with albuterol. Subjects will receive nebulized 3% saline (subjects with FEV₁ ≥ 35%) or normal saline (subjects with FEV₁ < 35%) for 20 minutes and will be encouraged to cough a minimum of every two minutes.

Intervention: The subjects will be instructed to use the study mouth rinse twice daily for 8 weeks. Subjects will be asked to swish 15 ml of study mouth rinse in their mouths for 30 seconds followed by expectoration. The study mouthwash must be used at least 30 minutes after eating and/or tooth brushing. This procedure will be performed in the morning and evening. Subjects will be instructed to not rinse with water or other mouthwashes, brush teeth, or eat immediately after rinsing for 1 hour. The subjects will be instructed not to ingest (swallow) the medication after rinsing. Subjects will be instructed to avoid: i) drinking tea to avoid tooth discoloration; ii) toothpastes containing the antimicrobial agent triclosan (list will be provided) and iii) mouthwashes other than the study drug. The participants will be asked to stop the study medication the night before the last clinic visit and to avoid routine dental clinic visit with cleaning during the study period.

Outcomes

[figure not shown]
Primary Outcome

Our primary outcome will be to compare the microbiota biomass of induced sputum and the oral cavity before and after 8 weeks of chlorhexidine rinse (n=25) compared to controls (n=25) using next-generation sequencing of the bacterial 16S rRNA gene.

Secondary Outcomes

Secondary outcomes will include: i) sputum and oral microbiota diversity; ii) sputum and oral microbiota taxonomy; iii) inflammatory markers hsCRP, fibrinogen, and leukocyte count; iv) BCSS score; v) SGRQ score; and vi) assessment of adverse effects.

Methods and Data Collection Plan

Medical History

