At the conclusion of the study, we will censor any subject who reports using systemic antibiotics during the 8-week study period. This will prevent antibiotic use from confounding our microbiota results. As this study is a randomized controlled study, the analysis for the primary outcome will consist of testing for differences in changes in bacterial biomass between the two patient groups using a 2 sample *t*-test with equal variances between groups. While it is widely recognized that the *t*-test is robust with regard to departures from the normality assumption, if the data appear very non-normal (as observed in a *qq*-plot) even after standard transformations are considered (such as the Box-Cox transformation) then Wilcoxon's test will be used. Similarly, if the variance is markedly different between the groups then Welch's 2 sample *t*-test will be used. While randomization should ensure that the groups are balanced on important potential confounders (such as age) all such factors will be examined to check that there are not significant differences between the groups. If there are differences then linear models will be fit to account for these potential confounders (again, standard transformations will be considered to improve model fit and diagnostics will be performed to assess model assumptions).

The analysis for secondary endpoints necessarily takes a different strategy as that investigates the relationship among variables that are not subject to direct randomization. Hence the analysis will consider regression models that investigate how changes in health status (as measured by changes in the SGRQ) depend on microbial diversity and inflammatory markers. Model selection will be guided by scientific plausibility, model diagnostics and measures of model quality (such as AIC).

Sample Size and Power Calculation

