We can use the preliminary data on microbial diversity among COPD patients to estimate the power of the study. For concreteness we will assess the power for detecting a difference in the Simpson (1-D) diversity measure (the correlation between this measure and Shannon's measure was 0.96 in our preliminary data). The standard deviation in this measure among moderately affected COPD patients is 0.280 and is 0.298 among the severely affected COPD patients, and as there is no significant difference between the variances ($p=0.80$ by Bartlett's test) we combine the data from both groups and obtain an estimate of 0.281 for the standard deviation. To obtain an estimate of the magnitude of differences that are reasonable to expect from a drug that decreases the diversity of the lung flora, we fit a linear regression model with diversity as the outcome and age as the predictor variable (the ages range from 55 to 78 among these subjects). Age has a significant positive impact on diversity ($p=0.047$)

with an estimated slope of 0.017, so that over the course of 20 years the model predicts that there will be a change of 0.34 in diversity. Hence we investigated the power for values of the difference attributable to the effect of chlorhexidine from 0.22 to 0.32 and present the results in Table 1 (these results are from a 2 sample *t*-test with equal variance using the estimated standard deviation from the previous study and 20 subjects per group). These results indicate that the study should have acceptable power if chlorhexidine has an impact on the diversity of the lung microbiota that is comparable to what is observed due to the effect of aging. We will increase the sample size to 25 per group since we anticipate censoring at least 20% of the subjects because of antibiotic use during the study. This population has a demonstrated exacerbation rate of approximately 20% and exacerbations are often treated with antibiotics.

Effect size	0.22	0.24	0.26	0.28	0.30	0.32
Power	0.67	0.75	0.81	0.87	0.91	0.94

Table 1: The power of the study to detect a difference between the treatment groups as it depends on the magnitude of the difference in diversity between the 2 groups.

Quality Control

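### Participants who report systemic antibiotics after randomisation are excluded (at least 20% expected), with no all-randomised analysis and no count of exclusions by arm, so the comparison can carry selection bias

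*Combined protocol and SAP*

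**What the plan says.** The Data Analysis Plan opens with the rule that "we will censor any subject who reports using systemic antibiotics during the 8-week study period", applied once the study has ended. The reason given is: "This will prevent antibiotic use from confounding our microbiota results". Sample Size and Power Calculation shows that removal from the analysis is meant. Power is computed on 20 per group, and 25 are enrolled because "we anticipate censoring at least 20% of the subjects because of antibiotic use during the study". The 20% is justified by one pooled figure: "This population has a demonstrated exacerbation rate of approximately 20% and exacerbations are often treated with antibiotics".

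Three other places bear on the point:

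- Efficacy of Oral Decontamination in COPD says that, if lung biomass falls, "this would be the basis for a large interventional trial to determine if oral decontamination with chlorhexidine will decrease COPD exacerbations".
- The exclusion criteria already list "Treated with antibiotics in the last 2 months".
- Study Intervention says "After 8 weeks of study drug, subjects will have all samples collected again", and antibiotic use is not among the reasons listed under Discontinuation of procedure.

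The document contains no analysis of all randomised participants, no sensitivity analysis that keeps antibiotic users, and no plan to tabulate antibiotic use or exclusions by arm.

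**The concern.** Antibiotic use during the 8 weeks comes after randomisation. If the rinse changes how often participants have exacerbations, it also changes who is removed, so antibiotic use may be a consequence of assignment and not a baseline confounder. Conditioning on it can make the retained arms differ in ways that randomisation had prevented. The fallback linear models adjust for factors such as age and do not address this. The allowance from 20 to 25 per arm covers lost precision only.

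If those who need antibiotics have worse values and more controls are removed, the retained controls look too good. A true chlorhexidine effect is then more likely to be missed, and false positives in its favour become rarer. The opposite relation reverses this. The documents support neither, and without counts by arm a reader could not tell which had happened.

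The scope is also unclear. The rule covers any subject, but its stated reason covers microbiota results only. Read literally, it would also drop participants from the "inflammatory markers hsCRP, fibrinogen, and leukocyte count; iv) BCSS score; v) SGRQ score" outcomes, for which the protocol gives no reason.

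**Working it through.** **The plan's own figures.** Inflation: 20/(1 − 0.20) = 25, as stated. Table 1 reproduces with an equal-variance t-test (noncentral t), 20 per arm and SD 0.281: 0.675, 0.749, 0.814, 0.867, 0.908, 0.939 against the printed 0.67, 0.75, 0.81, 0.87, 0.91, 0.94. The document states no significance level. Two-sided 5% is inferred because it reproduces the table. The sample-size arithmetic is therefore not in question.

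**Model for the bias (rates and correlations are assumptions).** Let Y be the outcome in SD units, higher being worse, and let antibiotic need be a standard normal variable with correlation r to Y. The fraction p with the greatest need is excluded. Then

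E[Y | kept] = −r·φ(c)/(1 − p), with c the (1 − p) quantile of the standard normal.

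- p = 0.30: c = 0.524, φ(c) = 0.3477, φ(c)/(1 − p) = 0.4967.
- p = 0.10: c = 1.282, φ(c) = 0.1755, φ(c)/(1 − p) = 0.1950.
- Bias, chlorhexidine minus control: r × (0.4967 − 0.1950) = 0.3017r.

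At 25% vs 15% the bias is r × (0.4237 − 0.2743) = 0.1494r. At 22% vs 18% it is r × (0.3796 − 0.3200) = 0.0596r.

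**Effect on the test.** At 30% vs 10%, 25 × 0.9 = 22.5 and 25 × 0.7 = 17.5 are kept, and the standard error is √(1/22.5 + 1/17.5) = 0.319 SD. The true effect for power is 0.909 SD, which gives 80% at 20 per arm. On the Simpson scale it is 0.909 × 0.281 = 0.255, between the 0.24 and 0.26 columns of Table 1. Power without bias is 79% at 30% vs 10% and 80% in the other rows. Unit SD is assumed among those kept.

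| Excluded, control vs chlorhexidine | r | Bias (SD, against chlorhexidine) | False positives in favour | False positives against | Power |
|---|---|---|---|---|---|
| 30% vs 10% | 0.1 | 0.030 | 2.0% | 3.1% | 77% |
| 30% vs 10% | 0.3 | 0.0905 | 1.3% | 4.6% | 71% |
| 30% vs 10% | 0.5 | 0.151 | 0.8% | 6.7% | 64% |
| 25% vs 15% | 0.3 | 0.045 | 1.8% | 3.4% | 76% |
| 25% vs 15% | 0.5 | 0.075 | 1.4% | 4.2% | 73% |
| 22% vs 18% | 0.3 | 0.018 | 2.2% | 2.8% | 78% |
| 22% vs 18% | 0.5 | 0.030 | 2.0% | 3.1% | 77% |
| 20% vs 20%, same selection | any | 0 | 2.5% | 2.5% | 80% |

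A negative r reverses the bias and swaps the two false-positive columns. A simulation of 60,000 trials, which allows for the smaller spread among those kept, gives power of 72% (r = 0.3) and 68% (r = 0.5) at 30% vs 10%. Because the primary outcome is a change, stable severity partly cancels and r may be nearer 0.1.

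**If the 20% exacerbation rate is annual.** The 8-week risk is 1 − 0.8^(8/52) = 0.034. Exclusions of 3.4% vs 1.7% give a bias of only 0.011 to 0.018 SD for r = 0.3 to 0.5.

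**Equal rates are not a guarantee.** If 20% leave each arm but the gap between excluded and retained participants differs by 0.5 SD between arms, the bias is 0.20 × 0.5 = 0.10 SD.

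**What an all-randomised analysis would cost in power.** Suppose antibiotics lower biomass by 0.5 or 1.0 SD (assumed) and use is 30% vs 10%. The contrast shifts towards zero by 0.20 × 0.5 = 0.10 or 0.20 × 1.0 = 0.20 SD. Simulated power for 0.909 SD, to within about 0.01:

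| r | Antibiotic-free | All randomised, 0.5 SD | All randomised, 1.0 SD |
|---|---|---|---|
| 0 | 0.79 | 0.79 | 0.63 |
| 0.3 | 0.72 | 0.82 | 0.69 |
| 0.5 | 0.68 | 0.84 | 0.74 |

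Neither analysis set has higher power throughout.

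**The case against.** The strongest reply is that the exclusion is a deliberate choice suited to a mechanistic pilot. It is pre-specified with a reason and a sample-size allowance, and it matches the baseline antibiotic exclusion. That stands: the antibiotic-free question is coherent and the analysis should be kept. It does not explain why this should be the only analysis.

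Second, the likely bias is modest. Even 0.15 SD is under half of the 0.319 SD standard error, every rate and correlation is assumed, and in the leading scenario the error is conservative for a claim of benefit. This stands as a limit on size. It does not tell a reader which scenario occurred.

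Third, the false-positive figures require chlorhexidine to leave biomass unchanged and still reduce antibiotic use. The protocol's route to fewer exacerbations runs through lower lung biomass, so another route, such as altered composition, would be needed. With a blinded placebo and no treatment effect of any kind, exclusions are equal in expectation. This weakens those columns but leaves the bias and power figures under a true effect intact.

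Fourth, Monthly calls names an antibiotic question only at week 4, and antibiotic users might not attend or produce sputum at week 8. The plan already relies on reported use over all 8 weeks, so this is a data-capture gap and does not block the fix.

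Finally, the scope point is the weakest part. The stated reason suggests a microbiota-only exclusion, and the Data Analysis Plan specifies no between-arm test of inflammatory markers, BCSS or SGRQ, although the aims imply one. It needs clarifying, but the main point does not depend on it.

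**Conclusion.** The concern holds and should be fixed. The plan removes participants on an event after randomisation that its own rationale links to treatment, expects to lose at least a fifth of them that way, and provides no second analysis and no counts by arm. What is established is the possibility of bias, not its size or sign. Under the assumed inputs it ranges from zero (equal removal that selects alike in both arms), through 0.01-0.02 SD if the 20% rate is annual and 0.04-0.07 SD at 25% vs 15%, to 0.09-0.15 SD at 30% vs 10% with correlations of 0.3 to 0.5. All results are in SD units because the documents give no SD for biomass, the primary outcome.

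**What to change.** 1. Add an analysis of biomass and the other microbiota outcomes in all randomised participants with a week-8 sample, by assigned arm. Report it beside the antibiotic-free analysis, and state in advance which is primary and what question each answers.
2. State the scope of the exclusion: limit it to microbiota outcomes and to models that use microbiota as a predictor. Keep all participants in any between-arm comparison of inflammatory markers, BCSS and SGRQ.
3. Report antibiotic use and exclusions by arm. An explicit antibiotic question at the final visit would make the weeks 4 to 8 count reliable.

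The cost is plan wording and one extra analysis of samples the protocol already collects. If the laboratory would otherwise skip the excluded samples, 20% of 50 is 10 participants, and 10 × 2 sample types × 2 visits = 40 assays. The drawback is that antibiotics add variance and may shift the all-randomised contrast towards zero, which is why both analyses should be reported.

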During the baseline visit, after obtaining informed consent, the medical history will be reviewed with the participant to make sure all key components of the past medical history, including dental history, are obtained for eligibility and safety purposes. The participant's electronic medical records will also be reviewed.

Medications/Supplement Use

Participants will be asked to bring all medications (prescription and non-prescription, including inhalers) with them to the study visit. All medications will be recorded and the VA medication dispensing records will also be reviewed electronically. In review of the subject's medications, the study team will be specifically looking for patients on antibiotics that may alter the microbiota. Non-prescription medications will be reviewed to make sure the patient is not taking over-the-counter mouth washes or toothpaste with triclosan that may alter the oral microbiota. The patient's respiratory and non-respiratory medications will not be altered as a part of this study.

Physical Examination

After informed consent and review of both medical and medication history, a member of the study team will perform a focused physical. The physical exam will focus on vital signs including resting oximetry, weight, and the oral and lung examination. At the final study visit the physical examination will be repeated.

St George's Respiratory Questionnaire (SGRQ)

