The sputum sample will be weighed and the oral wash volume will be measured. To identify the microbiota, DNA will be isolated from sputum and oral wash samples. Sputum samples will be treated with dithiothreitol (DTT) prior to isolation. We will use a previously described protocol for DNA isolation that includes bead beating to lyse bacterial cells, followed by precipitation with isopropanol and digestion with RNase. Samples will be subjected to PCR amplification using 16S rRNA gene primers specific to the constant regions flanking the V3 region[15, 29]. Amplicons will be gel purified and sequenced at the University of Minnesota Genomics Center using Illumina MiSeq equipment. To minimize effects of random sequencing errors, we will use RDP Pipeline to eliminate (a) sequences that did not appropriately match the PCR primer and the barcode at the beginning of a read, (b) sequence reads with <50 bases after the proximal PCR primer if they terminated before reaching the distal primer, and (c) sequences that contained more than one undetermined nucleotide (N). Both the proximal and distal primers will be trimmed from high-quality reads before database searches are performed.

Inflammatory Marker

To measure the inflammatory state, hsCRP, fibrinogen, and leukocyte count will be measured in blood.

Sample Banking

The microbiota studies will be performed at the University of MN. All remaining sample will be returned and stored in [name] laboratory at the VAMC. After completion, remaining sample will be stored for a maximum of 10 years for future confirmation studies and studies related to COPD. Samples will be de-identified and will be identified only by a pre-assigned sample ID number. Clinical data will NOT be given to the Univ MN laboratory.

Randomization procedure

Patients will be randomized via permuted block sizes of 2 to active drug or placebo in a ratio of 1:1. Because there is some evidence of an interaction with inhaled corticosteroids and the lung microbiota,

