we will stratify randomization according to use of inhaled corticosteroids at baseline. Only the Research Pharmacist will have access to the randomization list. The subjects will be instructed to use the study mouth rinse twice daily for 8 weeks as described above. The subjects will be asked to return all study medications at the last clinic visit. At the last visit the subjects will be asked whether they thought they were taking the active medication or placebo to assess the effectiveness of blinding.

The Breathlessness, Cough and Sputum Scale (BCSS)

The Breathlessness, Cough and Sputum Scale is an easy-to-use instrument for tracking the severity of respiratory symptoms and evaluating the efficacy of treatment in clinical trials in patients with COPD. It is designed as a daily diary in which subjects are instructed to answer three questions on a 0 to 4 scale, targeting breathlessness, cough and sputum. A total daily score is calculated from the question answers. This format allows investigators to assess symptom variability and trajectory over time. This tool has been validated in large clinical trials against the SGRQ[1, 2].

Monthly calls

Participants will be called at 4 weeks by the study coordinator to assess for: i) hospitalizations, ED visits; unplanned clinic visits; ii) new medication use including any systemic antibiotic use; iii) study drug compliance; iv) adverse events.

Effectiveness of blinding

At the last visit the subjects will be asked whether they thought they were taking the active medication or placebo to assess the effectiveness of blinding

Monitoring adverse events

Participants enrolled in this study will be monitored for adverse outcomes including adverse hospitalizations and death. Patients will be questioned during the mid-study telephone call and at the final study visit regarding any adverse drug reactions. In addition, participants will be given contact information for the study team and will be counseled to report any adverse effects. Participants will be questioned during the mid-study telephone call and at the final study visit regarding any hospitalizations. A report of every serious adverse event will be filed with the IRB per institutional policy. Electronic medical records will also be reviewed for 30 days after completing the study to capture any serious adverse outcomes, including hospitalization or death. If necessary, we will contact relatives or household members to obtain additional information.

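### The primary test is an unadjusted t-test on change that leaves out the ICS stratum and adjusts only after baseline significance checks; one prespecified ANCOVA per specimen would usually be more precise

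*Combined protocol and SAP*

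**What the plan says.** - **Primary test.** The Data Analysis Plan specifies "testing for differences in changes in bacterial biomass between the two patient groups using a 2 sample" t-test with equal variances. Standard transformations are to be considered if the data look non-normal, Wilcoxon's test is used if they remain so, and Welch's test is used if the variances differ markedly. No numerical threshold is given for any of these switches.
- **Covariates.** Age is the only potential confounder named, as an example. The plan says "all such factors will be examined to check that there are not significant differences between the groups", and then "If there are differences then linear models will be fit to account for these potential confounders".
- **Stratification.** Under Randomization procedure, allocation uses "permuted block sizes of 2 to active drug or placebo in a ratio of 1:1". The reason for stratifying is given as "Because there is some evidence of an interaction with inhaled corticosteroids and the lung microbiota", so "we will stratify randomization according to use of inhaled corticosteroids at baseline". The Data Analysis Plan mentions neither ICS nor the stratum.
- **Specimens.** The Overview under Work Proposed defines the primary outcome as biomass "in the COPD lung and oral cavity as measured in induced sputum and oral wash". Two specimens are therefore primary, but no model is written for either.
- **Sample size.** Table 1 is calculated for 20 subjects per group. Enrolment is 25 per group to allow for excluding at least 20% because of antibiotic use.

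**The concern.** Four features of the primary analysis can be improved.

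1. **Change score without baseline.** Subtracting baseline fixes its coefficient at 1. When the SDs are similar at both visits, estimating the coefficient gives a more precise comparison unless r is very high.
2. **Stratum left out.** The protocol thinks ICS use important enough to stratify on, yet the analysis ignores it.
3. **Adjustment triggered by significance.** In a randomised trial, a significant baseline difference is a chance event and says nothing about whether the factor predicts outcome. The rule will almost never select ICS, because stratification balances it, while an irrelevant factor can enter by luck.
4. **Choices made after seeing data.** Scale, test and covariates all remain open, separately for each specimen, so more than one primary p-value could be defended.

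At stake is precision in a trial expecting about 20 analysable subjects per arm, and a primary result that can be traced to one prespecified model.

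**Working it through.** **Inputs from the documents:** 20 analysable subjects per arm; SD 0.281 and differences 0.22 to 0.32 (Simpson diversity, Sample Size and Power Calculation); blocks of 2 within ICS stratum; 20% exclusions.

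**Assumed, because the documents do not say:** two-sided 5% level; r from 0.3 to 0.8; an effect of 0.9 SD of log10 biomass. On the diversity scale Table 1 spans 0.22/0.281 = 0.78 to 0.32/0.281 = 1.14 SD, so 0.9 lies inside the plan's own range, though for a different endpoint.

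**Step 1: reproduce Table 1.** Noncentral t with 38 df and noncentrality d/(0.281·√(2/20)) gives 0.675, 0.749, 0.814, 0.867, 0.908 and 0.939. The table prints 0.67, 0.75, 0.81, 0.87, 0.91 and 0.94. The inflation also agrees: 20/(1 − 0.2) = 25.

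**Step 2: variances.** With baseline SD s0 and week-8 SD s8:

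- Var(change) = s0² + s8² − 2·r·s0·s8
- Var(ANCOVA) = s8²·(1 − r²)
- Difference = (s0 − r·s8)², which is never negative

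With equal SDs the ratio ANCOVA/change is (1 − r²)/(2(1 − r)) = (1 + r)/2: 0.65 at r = 0.3, 0.75 at 0.5, 0.85 at 0.7. (Table 1 puts a single-visit SD into a test of change. The two SDs coincide only when 2(1 − r) = 1, that is r = 0.5.)

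**Step 3: small-sample cost.** At N = 40 the ANCOVA variance is multiplied by 1 + 1/35 = 1.029 (ICS exactly balanced) to 1 + 2/35 = 1.057 (both covariates random), with 36 df. Break-even is r = 2/1.029 − 1 = 0.94 to 2/1.057 − 1 = 0.89.

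**Step 4: power at 0.9 SD and the effect detectable with 80% power, equal SDs (in SD units).**

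| r | Var(change) | Var(ANCOVA) | Power, change | Power, ANCOVA | Detectable, change | Detectable, ANCOVA |
|---|---|---|---|---|---|---|
| 0.3 | 1.40 | 0.91 | 0.65 | 0.81-0.82 | 1.08 | 0.88-0.89 |
| 0.5 | 1.00 | 0.75 | 0.79 | 0.87-0.88 | 0.91 | 0.80-0.81 |
| 0.7 | 0.60 | 0.51 | 0.95 | 0.96-0.97 | 0.70 | 0.66-0.67 |
| 0.8 | 0.40 | 0.36 | 0.992 | 0.994-0.995 | 0.58 | 0.55-0.56 |

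Simulation (20,000 trials per setting, pairs balanced within 24 ICS users and 16 non-users) agrees: 0.647 vs 0.817, 0.791 vs 0.882 and 0.951 vs 0.968 at r = 0.3, 0.5 and 0.7. At r = 0.5, ANCOVA with 20 per arm is worth 20/(0.75·1.057) = 25.2 to 20/(0.75·1.029) = 25.9 per arm on the change score.

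**Step 5: unequal SDs, r = 0.7, s0 = 1, effect 0.9 baseline SD.**

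| s8/s0 | Var(change) | Var(ANCOVA) | Power, change | Power, ANCOVA |
|---|---|---|---|---|
| 0.8 | 0.520 | 0.326 | 0.97 | 1.00 |
| 1.2 | 0.760 | 0.734 | 0.89 | 0.88-0.89 |
| 1.43 | 1.043 | 1.043 | 0.775 | 0.75-0.76 |

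The last row is the least favourable: s0 is about r·s8, the variances are equal, and ANCOVA pays only its small-sample cost.

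**Step 6: leaving out ICS.** In simulation (20,000 trials, r = 0.5, SD of change = 1), an ICS shift of 0.8-1.2 SD present at both visits cancels in the change score, and type I error stays at about 0.05. If ICS instead shifts the 8-week change by 0.5, 0.8 or 1.2 SD, type I error falls to about 0.042, 0.039 and 0.022. It is never inflated.

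**Step 7: the significance trigger.** With 50 randomised in blocks of 2 within stratum, 20% excluded at random and ICS prevalence 0.4-0.8 (assumed), a chi-square test at 5% selects ICS in 0.01-0.06% of 20,000 trials. Baseline biomass is selected in 5%. With 5 to 10 independent factors (the number is not given), at least one is flagged by chance in 1 − 0.95⁵ = 23% to 1 − 0.95¹⁰ = 40% of trials.

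**The case against.** The strongest reply is that nothing here is invalid. A two-sample t-test on change is a legitimate primary analysis for a pilot randomised trial, and no route to inflated type I error has been shown.

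The gain for biomass is also unknown: r, the biomass SDs and the ICS effect are not in the documents, and 0.9 SD is borrowed from the diversity scale. At r = 0.7 the power gain is about 2 points, at r = 0.8 it is under 1, and two of the three unequal-SD cases show none or a slight loss.

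The ICS omission may matter little. Under Medications/Supplement Use, patients' "respiratory and non-respiratory medications will not be altered as a part of this study", which favours a steady ICS effect that cancels in the change score.

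Lastly, the plan does name a default test and ordered fallbacks. A concrete version was simulated with assumed triggers: Shapiro p < 0.01 for Wilcoxon, variance ratio above 2.5 for Welch, and adjustment for any of baseline biomass plus five noise factors at p < 0.05. Type I error was 0.048-0.052 with test switching and 0.042-0.050 with conditional adjustment added.

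All of this stands as a limit on the point. The concern is one of efficiency and prespecification, and the 23-40% figure counts triggered adjustments, not false positives. Two things remain. The simulated rule needed thresholds that the plan does not supply, and it did not cover the choice of transformation. And with equal SDs the trade is lopsided: a material gain at low or moderate r against a slight loss at very high r.

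**Conclusion.** The concern holds as an improvement that should be made; it is not a validity flaw. The unadjusted change-score test usually gives up precision the trial could have from data it already collects. With equal SDs, 20 per arm and a 0.9 SD effect, the loss is about 16-17 points of power at r = 0.3, 8-9 at r = 0.5, 2 at r = 0.7 and negligible at r = 0.8. Beyond r of about 0.89-0.94, or with a baseline SD near r times the week-8 SD, ANCOVA is level or slightly worse. These figures are illustrative for biomass.

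Omitting ICS leaves the test at its nominal level or conservative. Its main significance is that the trigger rule cannot be relied on to bring in the one factor the protocol itself singled out. The openness of scale, test and covariates is a real gap in the text, but it is the weakest part of the point, and the recommended change does not depend on it. Confidence is medium because the key inputs are unknown.

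**What to change.** Replace the primary-analysis wording, before treatment codes are available to the analysts, with the following.

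- For each primary specimen (induced sputum and oral rinse), fit one linear model of log10 week-8 biomass on treatment arm, baseline log10 biomass and ICS stratum, tested two-sided at 5%.
- Report the adjusted difference as a fold change with a 95% confidence interval.
- State how the results for the two specimens will be read together.
- Take logs before any differencing, including in the sensitivity analysis on change.
- Delete the baseline significance checks and the adjustment that depends on them.
- Keep the change-score t-test, Welch or robust standard errors, and a rank-based analysis as named sensitivity analyses, so that the primary test does not switch.

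**Cost:** one paragraph and no new data, since baseline biomass and ICS use are already recorded. The model spends two degrees of freedom, about 3-6% of variance at 40 analysable subjects (1/35 to 2/35). The slight loss of precision described above is the only statistical downside.
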